3.2.3.2 Participants

Participants will be a non-clinical sample from the UK. Some of these participants will be from the 1.2.4 longitudinal tracking task and others will be new participants recruited from the North-East of England (predominantly Newcastle-Gateshead). Further details of numbers are provided in the next section (Protocol).

The criteria for inclusion in the testing is that the participant must be able to provide consent for taking part (thus ruling out serious cognitive impairments) and must be able to get to the location where testing will take place (thus ruling out certain serious physical impairments). There are no other exclusion criteria.

3.2.3.3 Equipment/Resources

To complete the intervention, a number of requirements are stated below. Some of these requirements are essential, while others are desirable. Contingency plans are discussed in the section dealing with risk management, below.

Requirement	Priority	Description	Responsibility
3-4 FriWalk devices	Essential	These devices should be available by September 2017.	UNITN
FriWalk navigation system	Essential	The FriWalk devices should be able to navigate several routes in a designated museum environment.	UNITN
FriWalk user interface for older adults	Important	An appropriate user interface for older adults to enable them to use the system.	UNITN

Table 6. Requirements for intervention study

CPSN recommendation system	Essential	System should be able to recommend activities to users.	ATOS + UNITN
FriTab user interface for older adults	Important	While an interface is available for the social network system, the FriTab version for older adults is important to encourage their use.	UNITN
Access to user data	Important	Experimenters should be able to access data from participating users' profiles in order to assess what recommendations they have seen, what they have accepted, and what they have liked.	ATOS

3.2.3.4 Protocol

There are two use cases matching the testing of the two different aspects of the system: the CPSN and the FriWalk itself. These are described below.

Use case 1: Using the social network

George is an elderly man who lives alone. While he sometimes finds out what is going on in the area, he would like to know about more events. When he is offered a chance to use the ACANTO CPSN, he is eager to try it. He enters his details into the FriTab API and will be presented with some recommendations. He finds one that he likes and decides to try it. The next day, he attends the recommended activity. His step counter records his physical activity and it can be seen that his physical activity has increased. At the event, he also meets several people and feels more socially involved as a result.

Use case 2: Using the FriWalk

Sandra is an elderly lady who lives alone. She has some difficulties with walking after having a fall several months ago. One day, she is invited to attend a session at the museum where she will use the FriWalk to get a guided tour. She decides that she will attend because the subject of the tour matches her interests. At the museum, she meets several other people who have come for the tour. A guide shows them how to use the FriWalk and they have a chance to ask any questions. After seeing how her FriWalk works, Sandra sets off with some other users. They take a tour about "The history of the North-East of England" and the FriWalk shows them where to go. At one point, Sandra decides that she needs to use the toilet. She presses a button requesting guidance to the toilet and the FriWalk shows her where to go. After returning from the toilet, the FriWalk guides her back to the group. At the end of the tour, Sandra is impressed with the system and decides to come back and try it again. She enjoyed using it and appreciated the interaction with other people in the group as they explored the features of the system.

Recruitment process (social network study)

Participants will be recruited from several sources: some participants are already engaged with longitudinal tracking for the ACANTO project, while others will be recruited fresh.

- 15 participants will be recruited from existing participants (i.e. longitudinal tracking, Task 1.2.4).
- 15 participants will be recruited from outside existing participants.
- 15 participants will be selected as controls (they will not use the social network).

Recruitment process (FriWalk study)

- 10 participants will be used to test the FriWalk to tour the museum.
- 10 participants will be used to have a non-FriWalk based museum tour.
- 10 participants will be selected as a control group (no tour, no FriWalk).

Scales

The objectives listed above provide the conceptual variables that need to be measured. What follows is how we propose to measure them.

Control variables

Each of the control variables are taken from the UTAUT scale (Morris et al. 2003) and the items will be adaptations (for the ACANTO system) of these items. In the case of the social network testing, we will also ask about their engagement with the system to control for participants who were less interested in the system.

Variable	Scale/measure		
Perceived social involvement	Three items asking about the extent of perceived social involvement, its quality, and its enjoyability.		
Actual social involvement	In participant diaries, participants will list who they met during the day from outside the people who live in their home (1 item). This should be corroborated with data from the social network system.		
Quality of recommendations	Several items asking about the personal relevance of the recommendations, the liking of the recommendations, and the ability to do the recommendations.		
Turnout to experimenter- organised event	Number of people who attend event (recorded by experimenter)		
Liking of participants for one another	Several items asking to what extent they perceive others in the group as similar and the extent to which they like them.		
Physical activity	Number of steps taken as measured by step counters		
Well-being	Personal wellbeing index (International Wellbeing Group 2013)		
Perceived sleep quality	Pittsburgh Sleep Quality Index (Buysse et al. 1989)		

Table 7	. Social	l networl	k testing
---------	----------	-----------	-----------

Table	8.	Fri	Walk	testing
-------	----	-----	------	---------

Variable	Scale/measure	
Physical activity	Steps from step counters	
Fear of falling	Falls Efficacy Scale International Short form (Kempen et al. 2008)	
Anxiety about attending event	Several items asking extent to which the user feels anxious about attending events outside the home (baseline) and the extent to which they feel anxious attending events where a FriWalk is available. Anxiety will be asked with reference to (a) finding their way around the environment and (b) having physical support.	
Sense of common identity	Two items adapted from Drury, Cocking, & Reicher, (2009) asking about a sense of unity within groups.	
Well-being	Personal wellbeing index (International Wellbeing Group 2013)	
Time taken to find facilities	Comparison of time taken between participants who do not use the FriWalk to find facilities and those who do use it (given unfamiliarity with the environment).	
Sleep quality	Pittsburgh Sleep Quality Index (Buysse et al. 1989)	
Willingness to return	Several items asking about whether the participant would come back to the museum for a similar tour using the FriWalk.	

Phases

The following is a brief outline of the phases involved in collecting data for the social network trial.

Table 9. Phases of social network study

Phase 1: Ethics and Recruitment			
Ethical approval	Ethical approval forms should be completed and approved		
Recruitment	Recruitment of 30 participants and invitation to try the system.		
	Phase 2: Pilot study		
Seeding system with	Experimenters will add activities to the system from the surrounding area and		
recommendations	will tag these appropriately.		
Checking system	Experimenters and some participants will check that the system is working		
	properly.		
	Phase 3: Testing		
Initial workshop	Participants will be invited to a workshop where the system will be explained		
	to them and where they will enter their data. At this initial session,		
	participants will be given a diary to complete during the next 2 weeks. The		

	diary will contain questions about their social involvement. They will also be given step counters and will also be asked to complete a short questionnaire for baseline measurement. For practical purposes, this workshop may be split into two or three workshops (given participant availability).	
Using the network	Participants will use the FriTab API for a period of 2 weeks.	
Control group	An additional 15 participants (control group) will be asked to complete diaries and carry step counters for 2 weeks.	
Test event	To test the system, the experimenters will run an interactive workshop and will advertise it via the ACANTO social network. The topic of this workshop is to be decided, but it may be something like, "A guide to smartphones for the older user." The activity will be tagged with relevant tags (e.g. "technology", "internet") and users who express these interests should receive a recommendation for the workshop. Turnout will be monitored at the event and liking for others in the group will be assessed.	
Return and debrief	After the 2 weeks, all participants will return and be debriefed on the purpose of the study. Additional measures will be taken via a short questionnaire (to see changes from the questionnaire administered at the start of the study).	

Table 10. Phases of FriWalk study

	Phase 1: Ethics, recruitment and collaboration
Ethics	Ensure ethical approval is obtained from UNAN ethics procedure
Recruitment	Recruit interested participants to take part in the FriWalk trial.
Collaboration	Collaboration with museums to implement FriWalk devices in the environment.
	Phase 2: Pilot testing
Testing at UNAN	Devices will be set up on UNAN premises and participants will be invited to try out the devices. Data will be collected about users' average walking pace to assist with matching participants for the museum trial.
Baseline tracking	Participants will be given diaries and step counters to monitor their baseline activity.
	Phase 3: Museum testing
Museum tour start	 Participants will be invited to a tour of a museum where they will be given a FriWalk. Approximately 4 participants will be in each group, assuming that 4 FriWalk devices will be available. Each group will be tested on separate days. Some of these events may be advertised via the social network system. Participants may be matched based on their average walking pace or ability.

Pre-tour questionnaire	Questionnaires will be completed before the tour.
Tour	The tour will involve a programmed route during which the FriWalk will guide the user around the museum. An experimenter will accompany the participants.
Post-tour questionnaire	After the tour, a questionnaire will be completed to ask about the experience.
Control group	A tour will be arranged without the FriWalk and will act as a control group. Questionnaires will be completed before and after.
Second control group	Participants in the no-tour, no-FriWalk group will attend the university to provide answers to a questionnaire.

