Then for the testing of the *FriWalk*. We intend to organise several events where users will come to a museum to test the FriWalk devices. It will involve an administrator/experimenter setting up an event and inviting users to come to the event. Users may be selected based on their stated interests (e.g. history) and may be matched based on their performance abilities (e.g. speed of walking). The experimenter will collaborate with a museum to arrange the event. UNAN has numerous museums that may be available for collaboration (e.g. Centre for Life, The Great North Museum, the Discovery Museum, or Segedunum Roman Fort).

The outcome measures are:

- 1. Physical activity
 - a. Step count: there should be an increased number of steps as a result of taking part in the activity
- 2. Psychological confidence
 - a. Fear of falling: Reduced fear of falling when using the device. This will be measured at baseline (T 1.2.4 questionnaires).

- b. Less anxiety about going out to attend an event where the FriWalk will be used
- 3. Social and emotional bonding
 - a. Sense of common identity: Social bonding/sense of shared identity as "FriWalk user group"
 - b. Increased perceived wellbeing as a result of shared identity (C. Haslam, Cruwys, and Haslam 2014; S. A. Haslam et al. 2009)
- 4. Improved ability to use the museum
 - a. Time taken to find facilities: it should be quicker for users who are unfamiliar with the environment to find facilities when they have the FriWalk.
- 5. Improved sleep quality
 - a. Subjective sleep quality: this should increase as a result of increase physical activity (see above (3b) for the rationale).

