3.2.6 Plan for statistical analysis

A variety of statistical methods will be used to analyse the data. Regression analysis will be used to model the effects of using the social network system (acceptance of recommendations) on outcome measures such as social and physical activity. This will allow other measures such as attitudes to the system or engagement with the system to be controlled for.

ANOVA (analysis of variance) tests will be used to assess differences between groups in the CPSN (social network users vs. non-users and pre-trial vs. post-trial) and in the FriWalk testing (experimental groups vs control groups). These will also allow for the testing of interaction effects to see whether the use of the walker interacts with other measures (e.g. fear of falling or frailty) on the effects of the intervention (such as increased confidence or increased physical activity).

4 Ethical approval

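### Social network study: 30 invited users are compared with 15 separately selected controls, and the planned pre/post comparison and regression do not remove the resulting selection bias; FriWalk-study allocation is unstated

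*Protocol*

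**What the plan says.** **Social network study.** Protocol 3.2.3.4 lists three sets of people: "15 participants will be recruited from existing participants (i.e. longitudinal tracking, Task 1.2.4"), "15 participants will be recruited from outside existing participants", and "15 participants will be selected as controls (they will not use the social network"). Table 9 gives the order. Phase 1 is "Recruitment of 30 participants and invitation to try the system". The controls appear later, under testing: "An additional 15 participants (control group) will be asked to complete diaries and carry step counters for 2 weeks". No source or selection rule is given for them.

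**FriWalk study.** The same section names 10 people for a FriWalk tour, 10 for an ordinary tour, and "10 participants will be selected as a control group (no tour, no FriWalk"). How people reach each group is not stated. Table 10 describes one recruitment of interested volunteers. Section 3.2.3.1 adds "Users may be selected based on their stated interests (e.g. history"), with optional matching on walking ability.

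**Analysis and claims.** Section 3.2.6 states that "ANOVA (analysis of variance) tests will be used to assess differences between groups in the CPSN". The sentence goes on to name both users against non-users and before against after the trial, and then experimental against control groups for the FriWalk. It also plans a regression that controls for attitudes to, or engagement with, the system. Sections 3.2.3 and 3.2.3.1 expect users to be more active and more socially involved because of the system, both over time and against controls.

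**The concern.** People who accept an invitation to try a social network are likely to differ from people picked as non-users in sociability and activity, which are the outcomes themselves. If so, a user v non-user difference mixes the effect of the system with the effect of who was invited and agreed.

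The conclusion carries weight beyond the study. Section 3.2.1 argues that showing the social scenario to be effective, together with the clinical findings, lets benefit be assumed to some extent in a combined setting that will not be tested. Allocation is also a design decision, which no later analysis can fully repair.

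**Working it through.** The social trial states no sample-size calculation, effect size or SD, so there is no figure to reproduce. The check has two parts.

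**1. Do the planned safeguards remove the selection problem in the network study?**

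- *Pre/post factor (3.2.6).* A group-by-time analysis cancels a stable baseline difference, provided both groups have a baseline. Table 9 places the baseline questionnaire at the workshop where users are shown the system. For controls it describes only two weeks of diaries and step counters.
- *Steps and diaries.* Section 3.2.3.1 wants steps compared with the person's own activity in a comparable period without the intervention. Table 9 schedules no such period. Diaries and counters are handed out at the workshop for the following two weeks, use of the network lasts two weeks, and participants return after the two weeks. On the natural reading these are the same two weeks, so the step and diary results rest on the between-group contrast.
- *Regression (3.2.6).* Engagement arises after exposure and non-users have none. Adjusting for it does not adjust for who was chosen.
- *What pre/post cannot cancel.* Even with complete baselines, different trends and regression to the mean would remain.

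**2. Illustration of size**

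Inputs from 3.2.3.4: 15 + 15 = 30 users v 15 controls (45 in all); 10 + 10 + 10 = 30 in the FriWalk study. Assumptions: no system effect; a pre-existing difference *b* in SD units; a post-only two-group t-test; two-sided alpha 0.05. That level is stated only for the clinical trial (3.1.4).

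Formula: the test statistic is non-central t with *n1* + *n2* − 2 degrees of freedom and non-centrality *b* / √(1/*n1* + 1/*n2*).

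- 30 v 15: √(1/30 + 1/15) = 0.316, 43 df. For *b* = 0.3 and 0.5 the non-centrality is 0.95 and 1.58.
- 10 v 10: √(2/10) = 0.447, 18 df. For *b* = 0.3 and 0.5 it is 0.67 and 1.12.

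| Assumed *b* (SD) | 30 v 15 | 10 v 10 |
|---|---|---|
| 0 | 5.0% | 5.0% |
| 0.2 | 9.5% | 7.1% |
| 0.3 | 15.3% | 9.7% |
| 0.5 | 34.0% | 18.5% |
| 0.8 | 69.6% | 39.5% |

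The FriWalk study has three groups. A one-way 10/10/10 ANOVA with one group shifted by 0.2, 0.5 or 0.8 SD rejects in 6.8%, 17.8% or 39.9% of studies.

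**After randomising the same people**, the expected pre-existing difference is zero and the rate returns to 5%. Precision does not change. By normal approximation, 80% power needs (1.960 + 0.842) × 0.316 = 0.89 SD for 30 v 15, and 2.802 × 0.447 = 1.25 SD for 10 v 10.

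**The case against.** The strongest reply is that this is a controlled before/after design, not a bare comparison of two groups. Section 3.2.6 names the pre/post contrast, and 3.2.3 names a longitudinal comparison. All participants share the entry criteria in 3.2.3.2. Table 9 has all participants return for a questionnaire meant to show change from the start, which may imply that controls had one too. These are small user studies, and the therapeutic claim rests on the separate, block-randomised clinical trial.

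Much of this stands, and it rules out three stronger readings.

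- *That the planned analysis would give false positives in 15% to 34% of studies.* Those figures belong to a post-only test with a stable shift, and a complete group-by-time analysis would cancel exactly that shift. What would remain is differential change, for which the documents give no figure.
- *That the FriWalk groups are stated to be non-random.* Section 3.2.3.4 is silent, and Table 10 fits one willing pool later split in three. Interest-based selection concerns invitation to museum events; nothing says it separates FriWalk users from ordinary-tour controls, and both of those groups attend a tour. Table 10 also includes baseline step and diary tracking, and questionnaires before and after both tours.
- *That drawing half the users from the tracking cohort proves imbalance.* The controls' source is not given, so it cannot.

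The reply does not rescue the network study. Its split into 30 invited users and an additional 15 selected controls is explicit, and the pre/post protection is incomplete as Table 9 describes it. In the FriWalk study the no-tour group is likewise described only as answering a questionnaire at the university.

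**Conclusion.** The point holds for the social network study. Its groups are formed by invitation and selection, the between-group difference is credited to the system, and neither the pre/post factor as scheduled nor the regression removes the selection bias. The causal conclusion is stronger than the design supports, most clearly for steps and diary-recorded social involvement.

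For the FriWalk study the finding is weaker: allocation to the three groups of 10 is not stated, and selection by interest is allowed.

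The size of the bias is unknown. The ranges of 15% to 34% (30 v 15) and 10% to 19% (10 v 10) are illustrative and rest on an assumed 0.3 to 0.5 SD shift, a post-only two-group test, and a 0.05 level taken from the clinical trial. The clinical trial itself is not affected.

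**What to change.** **Social network study.**
- Recruit all 45 under one invitation that explains both groups.
- Randomise 2:1 to network or control, stratified by source (tracking cohort or new).
- Give controls the same baseline questionnaire as users.
- Analyse by allocated group with adjustment for baseline.

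Cost: a random list, a reworded invitation, and one short questionnaire for the 15 controls. Total and group sizes do not change. The small downside is that some recruits will be told they are controls; they can be offered the system after the debrief.

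**FriWalk study.**
- State the allocation method.
- Complete any selection by interest first, then randomise the 30 recruits 1:1:1 to FriWalk tour, ordinary tour or no tour.
- Do not stratify by walking pace under the present schedule. Table 10 collects pace while participants try the devices, so this would expose the no-FriWalk groups to the FriWalk. Pace stratification is possible only if pace is measured without the device, which means a separate assessment for all 30.

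If randomisation is not adopted in the network study, its user v non-user results should be reported as associations, not as effects of the system.

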 - a. Perceived social involvement: this should increase as a result of using the system, but will interact with the user's extent of use of the system. The more they use it, the more

benefits they will receive. Those who do not engage much with the system are not expected to show benefits.

- b. Actual social involvement: by using participant diaries, we will show the effect of using the social network on actual involvement.
- c. Quality of recommendations: the more that a user discloses to the system, the greater the quality of the recommendations.
- d. Turnout to event: users who are more engaged with the system and who perceived higher quality of recommendations will be more likely to attend an event to which they are invited. This event will be organised by the experimenters and numerous people will be invited.
- e. Liking of the participants: At the event, liking for each other will be greater depending on the number of similar interests as recorded by the system compared to groups whose members have been randomly selected (similarity-attraction hypothesis; Byrne, 1972).
- 2. Physical activity
 - a. Number of steps taken: as a result of being more socially involved and attending an event, participants should show an increased number of steps compared to their own pattern of activities in a similar period without the intervention. They will also show more steps compared to a control group who do not take part in the intervention.
- 3. General well-being
 - a. Well-being: as a result of having more physical activity, users should show increased levels of subjective well-being (Netz et al. 2005).
 - b. Perceived sleep quality: this should increase as a result of having more physical activity. We know that sleep quality is affected by physical activity (King et al. 1997; Sherrill, Kotchou, and Quan 1998) and that sleep is linked to poor health outcomes (Strine and Chapman 2005). Therefore, it is an important finding if physical activity can increase sleep quality through use of the ACANTO system.

Outcome measures (FriWalk)

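### Table 9 lists the debrief on the study's purpose before the closing questionnaire, and nothing in the protocol requires the questionnaire to come first

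*Protocol*

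**What the plan says.** Protocol section 3.2.3.4, Table 9, sets out the social-network study in phases. At the initial workshop, "Participants will be invited to a workshop where the system will be explained" to them; in the same session they "will also be asked to complete a short questionnaire for baseline measurement". They also receive step counters, and "participants will be given a diary to complete during the next 2 weeks".

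After two weeks of use and a test event, the row headed Return and debrief says that "all participants will return and be debriefed on the purpose of the study. Additional measures will be taken via a short questionnaire". The purpose of that questionnaire is given as "to see changes from the questionnaire administered at the start of the study", so it is the post-trial measure.

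Table 7 in the same section defines the outcomes. Perceived social involvement, for example, is measured by "Three items asking about the extent of perceived social involvement, its quality, and its enjoyability". The hypothesis in section 3.2.3.1 has a direction: "Perceived social involvement: this should increase as a result of using the system". Section 3.2.6 plans analysis of variance for users against non-users and for pre-trial against post-trial. No section says that the closing questionnaire is completed before the debrief.

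**The concern.** A participant who has just been told what a study is for may, without meaning to, shade a subjective rating towards that purpose. These ratings come from people who know whether they used the network, and the hypotheses point one way. The closing visit as listed puts the disclosure directly ahead of the ratings.

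If staff follow that order, the change in users' questionnaire scores mixes any effect of the system with any effect of the debrief. No later analysis can separate the two within the users' pre/post change. The comparison of users with controls is distorted as well if the two groups react differently to the debrief.

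**Working it through.** **Step 1. Order of the closing visit.** In the Return and debrief row, the debrief comes in the first sentence and the questionnaire in the second. No linking word fixes the sequence. Table 9 is the only operational description of this visit. For the museum study, by contrast, Table 10 ties its questionnaires explicitly to before and after the tour.

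**Step 2. Which outcomes could be exposed.** The protocol does not list the questionnaire's content, so the eight outcomes of Table 7 are sorted by where each is collected.

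| Outcome | Self-reported? | Where collected | Exposed to the debrief? |
|---|---|---|---|
| Perceived social involvement | Yes | Not stated; by elimination the questionnaires | Yes |
| Actual social involvement | Yes | Diary during the two weeks | No |
| Quality of recommendations | Yes | Not stated | Probably |
| Turnout | No | Recorded by the experimenter | No |
| Liking of others | Yes | At the test event | No |
| Physical activity | No | Step counter | No |
| Well-being | Yes | Not stated; by elimination the questionnaires | Yes |
| Sleep quality | Yes | Not stated; by elimination the questionnaires | Yes |

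Self-reported: 8 − 2 = 6. Collected before the return visit: 2. Exposed: at most 6 − 2 = 4. The technology-acceptance (UTAUT) items, which section 3.2.3.1 treats mainly as control variables, are probably in the questionnaire too.

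**Step 3. Which comparisons are affected.** Let b_U and b_C be the shifts, in SD units, that the debrief adds to the answers of users and controls.

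- Users, pre/post: bias = b_U, because only the second measurement follows the debrief.
- Users against controls: bias = b_U − b_C, which is zero if both groups shift equally.

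For controls, Table 9 mentions only diaries and step counters during the two weeks and no starting questionnaire. As written, the pre/post change on these scales may therefore exist for users only, and that is the more exposed comparison.

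**Step 4. Illustration of size.** The plan gives no figure to reproduce.

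- From section 3.2.3.4: 15 + 15 = 30 users and 15 controls.
- Assumed: no true effect; b_U = 0.2, 0.3 or 0.5; b_C = 0; pre/post correlation r = 0.5, so that the SD of change is √(2(1 − r)) = 1; two-sided 0.05. Section 3.1.4 states 0.05 for the clinical trial only.
- Between groups: noncentrality = b_U / √(1/30 + 1/15) = b_U / 0.316, with 43 degrees of freedom.
- Pre/post in users: noncentrality = b_U × √30 = 5.477 × b_U, with 29 degrees of freedom.

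| Assumed b_U | Noncentrality, users v controls | Chance of a positive test | Noncentrality, users pre/post | Chance of a positive test |
|---|---|---|---|---|
| 0 | 0 | 5% | 0 | 5% |
| 0.2 | 0.63 | 9.5% | 1.10 | 18.5% |
| 0.3 | 0.95 | 15.3% | 1.64 | 35.5% |
| 0.5 | 1.58 | 34.0% | 2.74 | 75.4% |

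A normal approximation gives similar values: 9.7%, 15.8% and 35.3% between groups, and 19.5%, 37.6% and 78.2% for pre/post. If controls shift as much as users, the between-group rate returns to 5% and the pre/post rates do not change.

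**The case against.** The strongest reply is that Table 9 is introduced as a brief outline and sentence order is not a timetable. The control-group row, for instance, follows the row on using the network although it appears to describe a parallel group. That stands: the text does not prove that the debrief will come first. What remains is that it lists the debrief first and contains no safeguard.

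A second reply is that users already know what the system is. It is explained to them at the workshop where the baseline questionnaire is taken, half of them come from the project's existing tracking study, and nobody can be blinded to using a social network. That lowers the additional effect of the debrief. It does not remove it, since a separate debrief on purpose suggests that something is left to disclose.

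Third, both key objectives, social involvement and physical activity, have measures that the debrief cannot reach: the diaries, which are to be corroborated with network data, and the step counters. This stands and limits the severity.

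A reader might infer that every self-reported outcome is contaminated, or that participants are told what the system should achieve. The documents support neither. The diary and liking items are collected earlier, and the text speaks only of the study's purpose, without saying that the expected direction of effect is disclosed.

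**Conclusion.** The point holds in a limited form. Read in the order written, Table 9 places the debrief ahead of the closing questionnaire. That opens up to four of the six self-reported outcomes in Table 7 to answers shaped by the disclosure. The users' pre/post comparison is exposed directly; the comparison with controls is exposed only if the groups respond differently.

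The percentages show direction and rough scale and are not estimates. They rest on assumed shifts, on no shift in controls (who are to be debriefed too), on an assumed correlation of 0.5, and on a significance level that the protocol does not set for the social trial. They also credit the whole shift to the debrief. A reader might go further and conclude that any positive result of this study could come from the debrief. That does not follow for steps, turnout, liking or diary-recorded contacts. This is a low-cost improvement to the protocol, not a must-fix.

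**What to change.** Reword the Return and debrief row of Table 9 so that each participant, user or control, completes and hands in the closing questionnaire, the diary and the step counter before being debriefed. It would help to name in the same row the scales that the questionnaire contains, so that the collection point of each Table 7 outcome is clear.

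If participants return on different days, those debriefed early could talk to those still to come. Holding back every debrief until the last questionnaire is in might then need a second contact, so it should not be made a requirement. Fuller disclosure can instead wait for the post-trial presentation and discussion already planned as milestone MS10 in section 3.2.4.

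The cost is a reworded table row, with no extra visit, staff or measurement. With the questionnaire first, the shift caused by a participant's own debrief is zero by construction. Participants remain unblinded, so other sources of reporting bias are unchanged.
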